2.3. Hypotheses

Primary Hypothesis

- At least 75% of the subjects who are classified by Quest questionnaire as being "discontented and driven" will be in the "likely to be successful" group. The Quest questionnaire will be collected at baseline.

Secondary Hypothesis

- At least one of the secondary endpoints will be significantly correlated with the success classification of the subjects after adjusting for age, sex and ADD power.

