14.2. Sample Size Justification

This is an exploratory study to generate initial data for assessing a computational vision model. As such, the sample size was not determined based on any power analysis with regard to the primary endpoint. The collected data will be used to design future studies, if necessary.

The planned sample size (75 to enroll and 50 to complete) was selected to enroll different categories of myopic presbyopes including previous MF CL wearers, Single vision CL wearers and Subjects who are neophyte to CL wear. Efforts will be made to enroll subjects in all three categories without specific targets to be achieved.

All analysis will be conducted on the per-protocol population defined in section 14.3.

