14.4. Level of Statistical Significance

All planned analysis for this study will be conducted with an overall type I error rate of 5%.

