14.5. Primary Analysis

Likelihood to be a successful lens wearer vs. Quest questionnaire classification

The successful lens wear will be converted to a binary response the same as in the previous analysis. The proportion of response (“1”) will be analyzed using a generalized linear mixed model with a binary distribution and logit link function for all questions. Each model will include the experimental design factors: Quest questionnaire classification as the fixed effect; and subject as the random effect. Other baseline characteristics known to be important such as age, sex, and/or add power will be included as fixed covariates when appropriate.

The proportion of successful lens wear for the subjects classified as being “discontented and driven” will be calculated with 95% CI for least square mean. If the lower limit of the CI is greater than 75%, the statistical superiority will be concluded.

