14.6. Secondary Analysis

Likelihood to be a successful lens wearer vs. physical ocular related measurements

The secondary analysis will be conducted using the same method as described in Section 14.5 regarding CLUE vision score at baseline. In the model the CLUE vision score at baseline will be replaced by the secondary endpoints (defined in Section 2.2) one at a time to determine the significance level of each physical ocular related measurement. If the measurement is taken by eye, average value of the left and right eye will be used.

Kenward and Roger⁶ method will be used for the calculation of the denominator of degrees of freedom.

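### Section 14.6 implies a Wald-type test in a logit model with one yes/no result per subject and no fallback for separated data; if failures are few, this gives up much of the power of a penalised-likelihood test.

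*Combined protocol and SAP*

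**What the plan says.** Section 14.5 analyses success with a "generalized linear mixed model with a binary distribution and logit link function", taking "Quest questionnaire classification as the fixed effect; and subject as the random effect". Section 14.6 carries this method over to the secondary endpoints, entered "one at a time to determine the significance level of each physical ocular related measurement". Left and right eyes are averaged, so there is one record per subject. It then states that the Kenward-Roger "method will be used for the calculation of the denominator of degrees of freedom"; the cited reference is a paper on restricted maximum likelihood.

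The secondary hypothesis in 2.3 is that at least one measurement is significantly related to success "after adjusting for age, sex and ADD power". Section 14.5 is softer and includes such covariates where appropriate.

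On numbers, 14.2 says "The planned sample size (75 to enroll and 50 to complete) was selected", and that "All analysis will be conducted on the per-protocol population defined in section 14.3". By 14.3 that population contains only subjects who completed every visit. By 2.2 a subject who did not complete all required visits is unsuccessful. The documents give no expected number of failures, no effect size and no power. The only success rate is the 75% benchmark in 2.3, which concerns one Quest class.

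**The concern.** A Wald test divides an estimated log odds ratio by its standard error. With few failures and several slopes, two things go wrong. A large effect inflates its own standard error faster than its estimate, so the statistic stalls. And some linear combination of the predictors may split successes from failures completely, in which case the maximum-likelihood estimate is infinite and the p-value carries no information. The plan does not say what would then be reported.

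A random intercept for subject does not help: with one binary value per subject its variance cannot be identified. The secondary hypothesis rests on these p-values, and 14.2 intends the data to inform later studies, so real predictors could be passed over because of the test chosen.

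**Working it through.** **No figure to reproduce.** The sample size is expressly not power-based, so the check is a simulation over assumed failure rates.

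**Inputs from the documents.** N = 50 planned completers (14.2); one predictor plus age, sex and ADD (2.3, 14.6), that is 5 parameters with the intercept; 5% level (14.4), taken here as two-sided per test.

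**Assumed inputs.** Failure rates of 10, 15 and 25%; odds ratio (OR) per SD of 2.7 to 4.5; N = 45 as well as 50, to allow for some loss. Expected failures = N × rate:
- 10%: 45 × 0.10 = 4.5; 50 × 0.10 = 5
- 15%: 45 × 0.15 = 6.75; 50 × 0.15 = 7.5
- 25% (the complement of the 75% benchmark): 45 × 0.25 = 11.25; 50 × 0.25 = 12.5

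**Tests compared.**
- Wald: t = b / SE(b) on N − 5 df. This is a stand-in for the Kenward-Roger F test, with the unidentifiable subject variance left out.
- Firth: maximise l*(b) = l(b) + ½ log|I(b)|, then refer 2[l*(full) − l*(predictor slope = 0)] to 3.84.

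**Power, adjusted models.** Relative loss = 1 − Wald/Firth. The N = 50 rows use 1,000 trials each (standard error at most √(0.25/1000) = 1.6 points) with covariates unrelated to outcome. The N = 45 rows use 1,500 trials each with modest covariate effects.

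| N | Mean failures | OR per SD | Wald | Firth | Relative loss |
|---|---|---|---|---|---|
| 50 | 5 | 3 | 30% | 45% | 33% |
| 50 | 5 | 4 | 40% | 59% | 33% |
| 45 | 4.5 | 2.7 | 18% | 35% | 49% |
| 45 | 4.5 | 4.5 | 30% | 60% | 50% |
| 50 | 7.5 | 3 | 57% | 64% | 12% |
| 50 | 7.5 | 4 | 67% | 78% | 14% |
| 45 | 6.8 | 2.7 | 37% | 49% | 24% |
| 45 | 6.8 | 4.5 | 57% | 75% | 24% |
| 50 | 12.5 | 3 | 74% | 76% | 4% |
| 50 | 12.5 | 4 | 90% | 92% | 2% |
| 45 | 11 | 2.7 | 60% | 64% | 6% |
| 45 | 11 | 4.5 | 87% | 91% | 4% |

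A separate run at N = 45 and OR 4.5 gave 28% vs 60% at about 4 failures, 57% vs 72% at about 7, and 85% vs 90% at about 11.

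**No finite fit.** For N = 45 to 50 and OR 2.7 to 4.5: about 17 to 29% of trials at 4 to 5 failures, 6 to 9% at about 7, and 2% or less at 11 to 12. Individual settings scatter a few points around these ranges.

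**Outer cases, OR 3.** At N = 50 with about 3 failures, 46% of trials have no finite fit and power is 10% vs 30%. At N = 40 power is 14% vs 35% at about 4 failures, 32% vs 50% at about 6, and 64% vs 70% at about 10.

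**What drives the loss.** The df adjustment does little: at N = 50 it moves the critical value from 1.96 to about 2.01 (45 df), and using z instead of t changed Wald power by only 1 to 5 points. The covariates matter: without them, at N = 50 and about 5 failures, at most about 2% of trials have no finite fit, and power at OR 3 is 43% vs 54%.

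**False positives, adjusted models with no effect (N = 40 and 50).** Wald rejected 0.4 to 1.7% at about 5 or fewer failures. Over failure rates of 6 to 25%, Firth rejected 2.3 to 4.9% and an ordinary likelihood-ratio test 6.5 to 14.3%. The unpenalised likelihood ratio is therefore not a safe substitute.

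**The case against.** Four stronger readings are tempting, and the documents do not support them.

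- **That failures will be very few.** No failure count is stated. If the 75% benchmark described the whole set, the loss would be 2 to 5 points. That benchmark is a threshold for one Quest class, however, and not a forecast for the analysed set.
- **That only 40 to 45 subjects will be analysed.** Section 14.2 plans for 50 completers. Smaller numbers are a sensitivity range.
- **That Kenward-Roger is the cause.** It signals which kind of test is planned. The loss comes mainly from the Wald statistic and from separated fits. Section 14.6 does not name the Wald test; it is inferred.
- **That the strongest predictors are the likeliest to be missed.** Wald power rises with effect size in every pair of rows above. What widens is the gap in power points to the penalised test, for example from 17 to 30 points at 4.5 failures.

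There are further fair points. The study is exploratory, and the Wald test errs on the conservative side. A more sensitive test does nothing about multiplicity, and the powers here are per test at 5%, whereas 14.4 sets 5% overall. Non-completers are failures by definition yet are left out of the analysis; settling that contradiction would raise the failure count and could shrink this problem. All of this stands, and it makes the point conditional. It does not remove it: 2.3 states a formal hypothesis of significance, no fallback is specified, and the penalised test had the higher power in every adjusted setting with a real effect, without exceeding 5% false positives.

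**Conclusion.** The point holds conditionally. Section 14.6 implies a Wald-type test on one binary result per subject and does not say how separated data are handled. For adjusted models with N = 45 to 50 and OR 2.7 to 4.5 per SD, the cost against a penalised-likelihood test is about one third to one half of the power at 4 to 5 failures, about one fifth at about 7, and 2 to 5 percentage points at 11 to 12. The low range is plausible because the completers-only set removes everyone who fails by not finishing; the remaining failures are completers with a poor vision or comfort rating or no investigator recommendation. The sizes rest on assumed failure rates and effects, on the three covariates being fitted, and on the Wald t test standing in for the Kenward-Roger F test.

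**What to change.** In 14.6, replace the mixed-model Kenward-Roger test by Firth penalised-likelihood logistic regression (PROC LOGISTIC with the FIRTH option, in the SAS version already planned). Use one record per subject and no subject random effect. Take p-values from the penalised likelihood-ratio test and 95% confidence intervals from the penalised profile likelihood. Report the odds ratio per SD with its interval for every measurement, not only its significance level, and state the range of failures expected in the analysed set.

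The cost is a short rewrite of 14.6, which is needed anyway because it refers to a CLUE vision score model that 14.5 no longer contains. No subjects or procedures are added. There are three limits. The secondary model will differ from that of 14.5. If dropout passes 15% and the multiple-imputation analysis of 14.9 is run, it must pool Firth estimates and standard errors, because likelihood-ratio p-values cannot be combined that way with PROC MIANALYZE. And multiplicity across the secondary endpoints still has to be dealt with separately.

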14.7. Other Exploratory Analyses

Not Applicable.

14.8. Interim Analysis

Not applicable.

14.9. Procedure for Handling Missing Data and Drop-Outs

Missing or spurious values will not be imputed. The count of missing values will be included in the summary tables and listings.

Subject dropout is expected to be one of the main reasons of missing data in this clinical trial. Past clinical trials don't provide the evidence that participant dropout is systematic or not-at-random. To evaluate the impact of missing data, sensitivity analysis will be conducted using multiple imputation methods if the proportion of participant dropout is greater than the 15%. The SAS/STAT procedures PROC MI and PROC MIANALYZE will be utilized with a parametric regression method used to make at least 5 imputations.

14.10. Procedure for Reporting Deviations from Statistical Plan

The analysis will be conducted according to that specified in above sections. There are no known reasons for which it is planned to deviate from these analysis methods. If for any reason a change is made, the change will be documented in the study report along with a justification for the change.

15. DATA HANDLING AND RECORD KEEPING/ARCHIVING

15.1. Electronic Case Report Form/Data Collection

The data for this study will be captured on electronic case report forms (eCRFs) using the Bioclinica EDC system. An authorized data originator will enter study data into the eCRFs using the EDC system. Data collected on equipment that is not captured in EDC will be formatted to the specification of the JJVC database manager and sent to JJVC for analysis. Data generated from interviews will be saved as audio files and any subsequent collation and tabulation of the interview notes will be organized in both Word and Excel files.

Where applicable, data print-outs from instruments will be marked with study and participant identifiers and retained in the participant record. If the print-out ink/paper are not stable, they will be photocopied, and the photocopy will also be retained in the participant record.

External Date Sources for this study include: Not Applicable

The clinical data will be recorded on dedicated eCRFs specifically designed to match the study procedures for each visit. Once completed, the eCRFs will be reviewed for accuracy and completeness and signed by the Investigator. The sponsor or sponsor's representatives will be authorized to gain access to the participant recordation for the purposes of monitoring and auditing the study.

Edit checks, electronic queries, and audit trails are built into the system to ensure accurate and complete data collection. Data will be transmitted from the clinical site to a secure central database as forms are completed or updated, ensuring information accuracy, security, and confidentiality. After the final database lock, the Investigator will be provided with Individual Patient Profiles (IPP) including the full audit trail on electronic media in PDF format for all of the study data. The IPP must be retained in the study files as a certified copy of the source data for the study.

The content and structure of the eCRFs are compliant with ISO14155:2011.¹

15.2. Subject Record

At a minimum, participant record should be available for the following:

- participant identification
- eligibility
- study identification
- study discussion
- provision of and date of informed consent
- visit dates
- results of safety and efficacy parameters as required by the protocol
- a record of all adverse events
- follow-up of adverse events
- medical history and concomitant medication
- test article receipt/dispensing/return records
- date of study completion
- reason for early discontinuation of test article or withdrawal from the study, if applicable

The participant record is the eCRF or an external record. The author of an entry in the participant record must be identifiable. The first point of entry is considered to be the source record.

Adverse event notes must be reviewed and initialed by the Investigator.

16. DATA MANAGEMENT

16.1. Access to Source Data/Document

The Investigator/Institution will permit trial-related monitoring, audits, IEC/IRB review and regulatory inspection(s) by providing direct access to source data/documents. Should the clinical site be contacted for an audit by an IEC/IRB or regulatory authority, JJVC must be contacted and notified in writing within 24 hours.

16.2. Confidentiality of Information

Information concerning the investigational product and patent application processes, scientific data or other pertinent information is confidential and remains the property of JJVC. The Investigator may use this information for the purposes of the study only. It is understood by the Investigator that JJVC will use information developed in this clinical study in connection with the development of the investigational product and therefore may disclose it as required to other clinical investigators and to regulatory agencies. In order to allow the use of the information derived from this clinical study, the Investigator understands that he/she has an obligation to provide complete test results and all data developed during this study to the Sponsor.

16.3. Data Quality Assurance

Steps will be taken to ensure the accuracy and reliability of data, including the selection of qualified investigators and appropriate clinical sites and review of protocol procedures with the Principal Investigator. The Principal Investigator, in turn, must ensure that all Sub-Investigators and clinical site personnel are familiar with the protocol and all study-specific procedures and have appropriate knowledge of the study article.

Training on case report form completion will be provided to clinical site personnel before the start of the study. The Sponsor will review case report forms for accuracy and completeness remotely during the conduct of the study, during monitoring visits, and after transmission to data management. Any data discrepancies will be resolved with the Investigator or designee, as appropriate.

Quality Assurance representatives from JJVC may visit clinical sites to review data produced during the study and to access compliance with applicable regulations pertaining to the conduct of clinical trials. The clinical sites will provide direct access to study-related source data/documents and reports for the purpose of monitoring and auditing by JJVC and for inspection by local and regulatory authorities.

17. MONITORING

The study monitors will maintain close contact with the Principal Investigator and the Investigator's designated clinical site personnel. The monitor's responsibilities will include:

- Ensuring that the investigation is being conducted according to the protocol, any subsequent amendments, and regulatory requirements are maintained
- Ensuring the rights and wellbeing of Subjects are protected
- Ensuring adequate resources, including facilities, laboratories, equipment, and qualified clinical site personnel
- Ensuring that protocol deviations are documented with corrective action plans, as applicable
- Ensuring that the clinical site has sufficient test article and supplies
- Clarifying questions regarding the study
- Resolving study issues or problems that may arise
- Reviewing of study records and source documentation verification in accordance with the monitoring plan

18. ETHICAL AND REGULATORY ASPECTS

18.1. Study-Specific Design Considerations

Potential Subjects will be fully informed of the risks and requirements of the study and, during the study, Subjects will be given any new information that may affect their decision to continue participation. Subjects will be told that their consent to participate in the study is voluntary and may be withdrawn at any time with no reason given and without penalty or loss of benefits to which they would otherwise be entitled. Only Subjects who are fully able to understand the

risks, benefits, and potential adverse events of the study, and provide their consent voluntarily will be enrolled.

18.2. Investigator Responsibility

The Principal Investigator is responsible for ensuring that the clinical study is performed in accordance with the signed agreement, the investigational plan, Section 4 of the ICH E6 guidelines on Good Clinical Practice (GCP),² and applicable regulatory requirements. GCP is an international ethical and scientific quality standard for designing, conducting, recording, and reporting studies that involve the participation of human Subjects. Compliance with this standard provides public assurance that the rights, safety, and well-being of study Subjects are protected, consistent with the principles of the Declaration of Helsinki 64th WMA General Assembly 2013³ and that the clinical study data are credible. The Investigator must maintain clinical study files in accordance with Section 8 of the ICH E6 guidelines on Good Clinical Practice (GCP),² and applicable regulatory requirements.

18.3. Independent Ethics Committee or Institutional Review Board (IEC/IRB)

Before the start of the study, the Investigator (or Sponsor when applicable) will provide the IEC/IRB with current and complete copies of the following documents (where applicable):

- Final protocol and, if applicable, amendments
- Sponsor-approved informed consent form (and any other written materials to be provided to the Subjects)
- Investigator's Brochure (or equivalent information) and amendments
- Sponsor-approved participant recruitment materials
- Information on compensation for study-related injuries or payment to Subjects for participation in the study
- Investigator's curriculum vitae, clinical licenses, or equivalent information (unless not required, as documented by IEC/IRB)
- Information regarding funding, name of the Sponsor, institutional affiliations, other potential conflicts of interest, and incentives for Subjects
- Any other documents that the IEC/IRB requests to fulfill its obligation

This study will be undertaken only after IEC/IRB has given full approval of the final protocol, amendments (if any), the informed consent form, applicable recruiting materials, and participant compensation programs, and the Sponsor has received a copy of this approval. This approval letter must be dated and must clearly identify the documents being approved.

During the study, the Investigator (or Sponsor when applicable) will send the following documents to the IEC/IRB for their review and approval, where appropriate:

- Protocol amendments
- Revision(s) to informed consent form and any other written materials to be provided to Subjects
- If applicable, new or revised participant recruitment materials approved by the Sponsor
- Revisions to compensation for study-related injuries or payment to Subjects for participation in the study
- Investigator's Brochure amendments or new edition(s)

- Summaries of the status of the study (at least annually or at intervals stipulated in guidelines of the IEC/IRB)
- Reports of adverse events that are serious, unanticipated, and associated with the test articles, according to the IRB's requirements
- New information that may adversely affect the safety of the Subjects or the conduct of the study
- Major protocol deviations as required by the IEC/IRB
- Report of deaths of Subjects under the Investigator's care
- Notification if a new Investigator is responsible for the study at the clinical site
- Any other requirements of the IEC/IRB

For protocol amendments that increase participant risk, the amendment and applicable informed consent form revisions must be submitted promptly to the IEC/IRB for review and approval before implementation of the change(s).

At least once a year, the IEC/IRB will review and reapprove this clinical study. This request should be documented in writing.

At the end of the study, the Investigator (or Sponsor where required) will notify the IEC/IRB about the study completion. Documentation of this notification must be retained at the clinical site and a copy provided to the CRO or Sponsor as applicable.

